## Study Procedures

Once informed consent is signed, the subjects will undergo the following procedures:

General and questionnaire: Data collected will include demographics, clinical symptoms, CFQ-R, and blood work. We will also collect history of other medical conditions, medications, and exacerbation history.

History and physical examination will be performed including vital signs and body mass index (BMI) will be recorded.

Pulmonary function testing will be performed according to American Thoracic Society recommendations. Participants will be asked to refrain from using short-acting bronchodilator drugs for at least 4 hours before testing and not take any long acting bronchodilator in the morning. Height, weight and oxygen saturation will be measured prior to these tests.

Blood and urine samples: Urine pregnancy test will be performed at all site visits. If positive, confirmation with serum pregnancy test will be obtained. Blood test for liver and renal function, inflammatory markers and blood levels of losartan and the metabolites EXP3179/EXP3174 will be drawn. A total of 30 cc (2 tablespoons) of blood will be collected at Visit 1 and visits 4, 5, and 7.

NPD measurement will be performed according to standard procedures (latest SOP of the Therapeutic Development Network of the CF Foundation). Double lumen nasal catheters with an external diameter of 2.5 mm will be used for measurements. One lumen will be filled with freshly prepared agar; the other lumen will be used for perfusion with different solutions. The agar catheter and subcutaneous bridges (metal butterfly needle system) will be made prior to use by warming 3% agar gel and injecting the solution into the catheter. They will be attached to 3M KCl/calomel reference electrodes (Baxter; Deerfield, IL) and connected to a bioamplifier system (AD Instruments; Colorado Springs, CO) for measuring and recording. The initial potential difference (PD) will be measured at the anterior tip of the inferior meatus. Then, the basal PD will be measured at various distances within the inferior meatus in each nostril. The nasal catheter will be fixed at the most negative potential in one nostril, and the test will be initiated using perfusion

with Ringer solutions until a stable value ( $\pm$  0.5 mV over 30 s) is obtained. Then, the nose will be rinsed with different solutions containing amiloride (to block ENaC), no chloride (stimulate flow through CFTR), and isoproterenol (activate CFTR). Finally, we will use ATP to increase the intracellular calcium concentration and activate CaCC. These tests will be repeated in the other nostril. De-identified NPD traces will be read at a central laboratory ([name] lab at Cincinnati Children's Hospital Medical Center (CCHMC) and [name] at University of Alabama at Birmingham (UAB)) blinded for the active or placebo arm.

**Nasal sample collection:** Nasal sample will be collected using Leukosorb as previously reported (14). In addition, we will obtain a small amount of nasal epithelial cells to measure TGF- $\beta$  by qPCR. De-identified samples will be sent to the Human Research Laboratory at University of Kansas Medical Center (KUMC) for analysis.

**Sweat test.** The sweat chloride test is a standard diagnostic tool for CF, serving as a biomarker of CFTR activity. Sweat samples will be sent to a central laboratory ([name] lab at CCHMC) for testing and interpretation of results. Individual sweat chloride test results will not be disclosed to the participants, with the exception of screening results. Specific instructions for collection, handling, processing, and shipping of sweat chloride samples to the local laboratory will be according to CFF guidelines.

### List of assessments (see Appendix 1)

## **EXPECTED RESULTS, LIMITATION AND DIFFICULTIES**

Given our preliminary data *in vitro* and *in vivo*, we expect that losartan increases functional CFTR recovery by OrkambiTM or SymdecoTM and possibly CaCC and BK function. We expect to see meaningful improvements not only in NPD but also in sweat chloride as well as decreases in hsCRP levels and other inflammatory markers locally and systemically (if elevated). We also expect improvements in CFQ-R scores.

The investigators have experience with executing clinical trials and with the measurements of the proposed endpoints. It is clear that there are several limitations: Even though power calculations (see below) indicate that the sample number should be sufficient to detect meaningful changes at least in the primary endpoint, the NPD and secondary endpoint signals need to be high enough to detect changes. Given the *in vitro* data, we are moderately confident that we will be able to detect these if present. The duration of the trial could be an issue (attrition), but our experience with adherence in clinical trials of this duration with CF patients indicate that this is not a limiting factor. We believe that allowing losartan to work as an anti-inflammatory for 3 months is important to counteract chronic inflammation in the airways. We will collect data that will indicate whether or not such an anti-inflammatory action actually occurs (even locally) and whether it is related to CFTR conductance changes. Secondary endpoints are purely exploratory however. If only trends are established, the data will lend itself to the design of a larger trial to fully explore the anti-inflammatory actions of losartan in CF patients.

## **Potential Benefits of the Proposed Research to the Subjects and Others**

There is no direct benefit to the subjects for participating on this study. Benefits for others may arise from data obtained in these studies to prevent and/or treat mucociliary dysfunction.

At the conceptual level, this project innovates by addressing airway inflammation with known properties of the commonly used, well tolerated, FDA approved medication losartan. At the therapeutic level, this project has the potential to add medical approaches for CF patients: the project could identify ARBs, and particularly losartan, as a "low hanging fruit" for treating CF patients by inhibiting TGF- $\beta$ 1 signaling to try to restore mucociliary transport and improve  $\Delta$ F508 CFTR restoring therapies. This approach is innovative since it avoids lengthy toxicity studies of new molecules and can be introduced into the clinic rapidly if successfully tested in clinical trials. Furthermore, the anti-inflammatory metabolite of losartan could stimulate the development of other, more potent anti-inflammatory molecules, and used for other airway diseases.

**Recruitment and Informed Consent:** Each site will recruit approximately 9 patients at the CF clinics. The study and informed consent form will be approved by the University of Miami's IRB. University of Miami IRB will serve as Central IRB and other Relaying IRBs will be the CCHMC, KUMC and UAB. Subjects will have sufficient time to meet with the PI and co-PIs to address all their questions about the research.

**Protection of Confidentiality:** No personal identifiers will be collected and each patient's data will be coded. There will be no names or other identifiers recorded on study data guaranteeing the success of these confidentiality measures (we will know age, gender and CF mutations).

## **STUDY DRUG: LOSARTAN**

Cozaar®, the commercial form of losartan is an FDA-approved ARB widely prescribed for treatment of hypertension, heart failure, and for renal protection in patients with diabetes. Losartan and matching placebo (25 mg or 50 mg pills/ placebo) will be compounded at each site by the research pharmacist and distributed to the subject based on the randomization table provided by the Biostatistician at University of Miami. Losartan/placebo will be given to the subjects by the PI or study coordinators free of charge. FDA has granted IND exemption for this study. The research pharmacist is responsible for maintaining accurate study drug accountability records throughout the study. Dose will be adjusted based on participant's weight at visit 1 as following: if participant's weight is  $< 55$  kg, participant will be randomized to either 25 mg or placebo. If participant's weight is  $\geq 55$  kg, participant will be randomized to either 50 mg or placebo.

Each dispensing of study drug will be documented in the subject's study records and in the drug accountability log. Subjects will return all unused study drug for drug accountability. Study drug will be destroyed at the research site as per the Institution regulations at the end of study.

Research pharmacists, UM biostatistician core and the assign unblinded monitor will be unblinded. Emergency plan for unblinding will be discussed with PI with consulting with the medical monitor and DSMB if necessary.

## **STATISTICS AND POWER ANALYSIS**

**Randomization:** Upon eligibility, a statistician randomizes all subjects in a 1:1 ratio to the placebo or losartan treatment group and informs the research pharmacy. Participants will be stratified by site during randomization.

**Design:** The basic study design consists of random assignment of patients to one of two treatment arms: losartan or placebo. Data will be collected at the visits as outlined above.

**Analysis:** Primary endpoint: A t-test will be used as preliminary data analysis. For the formal analysis, mixed effects models model will be used for analysis to accommodate the paired measures nature of the design, as well as missing values under the MAR assumption. We will determine the final analytic approach based on the final available data. Examination of baseline differences on key variables between subjects remaining and those lost-to-follow-up will also be conducted. The first set of analyses will not adjust for dropouts. Only cases with complete data will be included.

Secondary endpoints: Prior to analysis, we will investigate the distributional properties of the defined outcome measures - such as CaCC/BK activity, change in sweat chloride concentration, FEV1, changes in serum inflammatory markers, etc. Necessary transformations such as logarithmic or square root will be applied to satisfy normality assumptions if necessary. Baseline values of all variables will be examined, and estimates of baseline means and changes over time will be provided. The statistical analysis will consist of descriptive statistics associated with outcome measure (mean change or mean difference pre and post treatment) for two treatments. Means at baseline, 6 and 13/14 weeks, for each outcome, as well as the change over time will be provided, as well as the corresponding estimates of variability, and 95% confidence intervals will be constructed. t-tests for comparisons of the changes over the period between treatments will be conducted. However, the primary focus for this analysis is to obtain reliable estimates of the mean changes and variability, which will be useful for designing further investigation focused and specifically powered for comparing these outcomes. P-value will be significant if  $< 0.05$ . All tests will be two-tailed. The SAS statistical software package version 9.3 (Cary, NC) will be used for all statistical analyses.

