#### ADDITIONAL PRELIMINARY DATA

Additional preliminary data in patients show that Orkambi™ alone does not improve CFTR function *in vivo* as measured by nasal potential difference (NPD), possibly because of ongoing inflammation in CF patients. Given the small changes in sweat chloride, the same is true for Symdeco™. *In vitro* data show that:

- Losartan reverses the detrimental effects of TGF- $\beta$ 1 on ASL volume
- Losartan reverses the detrimental effects of TGF- $\beta$ 1 on CaCC and BK currents
- Losartan reverses the detrimental effects of TGF- $\beta$ 1 on lumacaftor-mediated F508del CFTR current recovery
- TGF- $\beta$ 1 has detrimental effects on tezacaftor-mediated F508del CFTR current recovery
- Decreases in ATP-induced PD are a measure of both CaCC and BK dysfunction.

- Losartan improved mucociliary dysfunction in a sheep model with CFTR inhibition and airway inflammation

These data make a compelling case for testing losartan as an anti-inflammatory medication in patients homozygous for F508del to improve the effects of Orkambi™ or Symdeco™ therapy on ion transport. Losartan will be given at least 12 weeks to assure that possible anti-inflammatory effects will have a chance to change the airway environment, since 4 weeks of treatment was insufficient in previous trials with other anti-inflammatory medications.

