## Study Design and Methods

**We propose to conduct a proof of concept clinical trial to test if administration of losartan augments CFTR function *in vivo* in patients who are on Orkambi™ or Symdeco™.** The goal of our pilot clinical trial is to examine the ability of losartan on CFTR (primary hypothesis) and possibly BK rescue/augmentation (secondary hypothesis) in patients homozygous for F508del on Orkambi™ or Symdeco™ therapy. The additional benefit for BK channels could be important but is harder to measure *in vivo*. Towards this end, however, we will assess CaCC/BK activity together as the response to ATP during NPD measurements, even though this is not an accurate reflection of either channel on its own.

**Note that ATP-induced changes in NPD in CF patients are higher than in normal subjects because *in vitro* data show that this response is increased in the *absence* of BK activity. Thus, the expectation here is that the rescue of BK activity with losartan will *DECREASE* NPD responses to ATP.**

**Primary hypothesis:** Losartan treatment for 12 weeks will improve CFTR conductance as measured by NPD in patients on Orkambi or Symdeco therapy. We expect that compared to placebo,  $\Delta$ NPD in response to 0 Cl/isoproterenol will change by more than -4 mV using the most polarized nostril each time.

**Secondary hypotheses:** Losartan treatment for 12 weeks will improve BK and CaCC activity as assessed by a decrease of changes in NPD to ATP exposure. Furthermore, losartan will reduce nasal cytokine levels and systemic inflammatory markers.

**Study plan:** Details are seen in Figure 2 and the study table. Briefly, 36 patients with CF, > 12 years of age, who are homozygous for F508del and have been on treatment with Orkambi™ or Symdeco™ for at least 3 months will be recruited for this trial. This trial will be randomized 1:1 with placebo (n=18 for each group). After signing informed consent at the screening visit, we will perform spirometry, determine sweat chloride, take blood (see below), and test for pregnancy where applicable. Since losartan has teratogenic effects, we will enforce strict birth control in female participants (see Potential Risk section.)

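### The primary analysis should prespecify site and background modulator, and report the losartan effect within each modulator as exploratory

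*Combined protocol and SAP*

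**What the plan says.** Study Design and Methods plans to recruit "36 patients with CF, > 12 years of age, who are homozygous for F508del" and who have taken Orkambi or Symdeco for at least 3 months. On allocation it says "This trial will be randomized 1:1 with placebo (n=18 for each group"). There is one primary hypothesis for both products: compared with placebo, the NPD response to zero chloride plus isoproterenol "will change by more than -4 mV using the most polarized nostril each time".

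The Background and the Protocol 3.1 summary of changes, which records the addition of Symdeco, justify pooling by the similar mode of action of the two correctors. Additional Preliminary Data lists losartan as reversing the TGF-β1 effect "on lumacaftor-mediated F508del CFTR current recovery". For tezacaftor it says only that TGF-β1 "has detrimental effects on tezacaftor-mediated F508del CFTR current recovery".

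Statistics and Power Analysis says "Participants will be stratified by site during randomization". It names a t-test as the preliminary analysis and a mixed effects model as the formal one, lists no covariates, and leaves the final approach to be settled on the available data. Neither site nor modulator appears in the analysis, and no estimate by modulator is planned. The significance level is 0.05 and "All tests will be two-tailed".

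**The concern.** The direct support for the primary hypothesis differs between the two products, and the product is known for every patient at entry because it is an inclusion criterion. An analysis that never mentions it raises two issues.

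- **Precision.** If NPD change differs between modulators or sites for reasons unrelated to losartan, leaving these factors out adds noise to a 36-patient comparison. Site is also the randomisation stratum, and the analysis would normally carry it.
- **Interpretability.** If losartan works less well with one corrector, the pooled estimate shrinks, and no planned display would let a reader see it. Because the final model is left open, a modulator term or split added later would be a post hoc choice.

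**Working it through.** **1. Evidence for each corrector (Additional Preliminary Data)**

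| | TGF-β1 impairs CFTR current recovery | Losartan reverses this |
|---|---|---|
| Lumacaftor | implied by the reversal; stated in the Background | reported, in vitro |
| Tezacaftor | reported | no result, positive or negative |

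**2. Inputs**

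From the documents: 36 patients, 18 per arm, a 4 mV difference (magnitude), two-sided 0.05, and about 9 patients per site, hence 36/9 = 4 sites. Assumed, because the text available gives no figure: the SD, the modulator split and the losartan effect with tezacaftor.

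The sample size of 36 cannot be reproduced without an SD or a power. The Endpoints section refers to a power calculation that the available text does not show, so no error in 36 is alleged. Solving backwards with SD = 4 / [(z₀.₉₇₅ + z_power) × √(2/18)]:

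- 80% power: 4 / [(1.960 + 0.842) × 0.3333] = 4.28 mV (4.16 by noncentral t)
- 90% power: 4 / [(1.960 + 1.282) × 0.3333] = 3.70 mV (3.60 by noncentral t)

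**3. Chance imbalance in modulator between arms**

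Hypergeometric, 18 of 36 allocated to losartan:

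| Patients on the less common product | Arms differ by ≥4 patients | Arms differ by ≥6 patients |
|---|---|---|
| 18 | 0.32 | 0.09 |
| 12 | 0.29 | 0.075 |
| 6 | 0.18 | 0.02 |

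With a near-even split, four sites of 9 and modulators mixed within sites, simulation with site strata gives 0.33 and 0.11. If modulator use follows site entirely, balance is nearly guaranteed. For a given imbalance d and a modulator shift m in mean NPD change, the unadjusted estimate moves by (d/18) × m. For d = 6 this is 0.33, 0.67 or 1.33 mV for m = 1, 2 or 4 mV. The documents give no value for m.

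**4. Effect of adjusting**

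Simulation: four sites of 9, near-even modulator split, SD 4.1, a 4 mV effect with both products.

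| Modulator shift | Power, unadjusted | Power, modulator in model |
|---|---|---|
| 0 mV | 0.81 | 0.80 |
| 2 mV | 0.78 | 0.80 |
| 4 mV | 0.71 | 0.80 |

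Type I error is 0.05 in every row, adjusted or not. With site in the model as well, the cost is about 1 to 2 points if neither factor matters, and the gain is about 7 points at a 4 mV modulator shift. If sites differ with an SD of 2 mV, the unadjusted test is conservative (type I error about 0.039, against 0.05 adjusted), and adjusting gains about 3 to 6 points.

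**5. Dilution**

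Pooled effect = (1 - f) × 4 + f × r × 4, where f is the tezacaftor share and r the fraction of the effect retained with tezacaftor. The power columns use the SDs that give 80% or 90% for a uniform 4 mV (4.16 and 3.60).

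| f | r | Pooled effect (mV) | Power, from 80% | Power, from 90% |
|---|---|---|---|---|
| 0.25 | 0 | 3 | 52–56% | 63–68% |
| 0.50 | 0 | 2 | 26–29% | 33–37% |
| 0.75 | 0 | 1 | about 10% | about 12% |
| 0.50 | 0.5 | 3 | about 55% | 67–68% |

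At SD 4.1, f = 0.5 and r = 0, simulated power is about 0.27 to 0.28 with or without the modulator term.

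**6. What estimates by modulator could show**

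With an even split there are 9 patients per arm for each modulator. At SD 4.16 the 95% CI half-width is 2.120 × 4.16 × √(2/9) = 4.2 mV. Power for 4 mV within one modulator is about 48% (SD 4.16) to 60% (SD 3.60). The standard error of the difference between the two effects is SD × √(4/9) = 2.77 mV at SD 4.16, so an interaction test for a 4 mV difference has about 30% power (39% at SD 3.60).

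**The case against.** The strongest reply has four parts.

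- **Pooling has a stated reason.** The correctors act similarly, TGF-β1 impairs both, and the proposed mechanism is that losartan counters TGF-β1. A reader might infer that the data show rescue only with lumacaftor and not with tezacaftor. The documents do not support that: the tezacaftor combination is unreported, not negative. This part stands in full.
- **The randomisation is defensible.** A reader might infer that modulator should have been a stratum. Four sites by two products gives 8 cells averaging 36/8 = 4.5 patients, so site alone is reasonable. This stands, and the gap lies in the analysis.
- **Imbalance may do little harm.** Patients have been on their modulator for at least 3 months and the formal model uses paired measures, so a stable difference in level largely cancels. Type I error is not inflated. This stands: at modulator shifts of 0 to 2 mV, modulator adjustment changes power by only 1 to 2 points.
- **A modulator term does not cure dilution,** and the subgroups are too small to settle it. This also stands.

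One might add that the plan does not exclude modulator, because it names no covariates and leaves the model open, and that medications are recorded, so a split could be produced at any time. That is true, but a split chosen after seeing the data carries less weight. The Expected Results section also says that trends will feed the design of a larger trial, which is where estimates by modulator would be useful.

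**Conclusion.** The gap is real but modest. The plan stratifies by site, yet prespecifies neither site nor modulator in the analysis and plans no estimate by modulator, although direct losartan evidence on CFTR current is reported for one corrector only. This is a matter of precision and interpretability. A reader might conclude that the comparison is biased or the pooling unjustified; neither follows.

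Adjustment is cheap insurance: a loss of about 1 to 2 points of power at worst in the cases run, against a gain of about 7 points for a 4 mV modulator shift at SD 4.1. It leaves dilution untouched. With no effect in half the patients, the pooled effect would be about -2 mV and power about 0.28 at SD 4.1, adjusted or not. Exploratory estimates by modulator would make a large difference visible but could not reliably separate a diluted effect from none. All these sizes depend on the assumed split, SD and tezacaftor effect, and should be read as ranges.

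**What to change.** In the analysis paragraph for the primary endpoint in Statistics and Power Analysis:

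1. State that the formal mixed model includes site (the randomisation stratum) and background modulator at Visit 1 (Orkambi or Symdeco) as prespecified fixed effects.
2. State that the losartan-placebo difference in NPD response will also be reported within each modulator with a 95% CI, labelled exploratory.
3. State that adjustment does not recover power lost to a diluted effect, and show the dilution calculation over a range of splits, SDs and tezacaftor effects.

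Leave the randomisation as it is.

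**Cost.** Wording only, since modulator is established at eligibility and medications are recorded. The model gives up four degrees of freedom (three for site, one for modulator). If modulator use clusters by site, the two terms will be partly collinear. The within-modulator intervals will be wide, about ±4 mV with 9 per arm at SD 4.16.

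### The plan leaves the final primary analysis to be chosen from the final data, with no rule, blinding or lock, so it does not guarantee the two-sided 5% level

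*Combined protocol and SAP*

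**What the plan says.** The Analysis paragraph of Statistics and Power Analysis makes four statements about the primary endpoint, in this order:

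- "A t-test will be used as preliminary data analysis". The variable it compares is not stated.
- The main model is then described: "For the formal analysis, mixed effects models model will be used for analysis to accommodate the paired measures nature of the design". A second reason given for it is that it copes with gaps in the data if these are missing at random.
- "We will determine the final analytic approach based on the final available data".
- After a planned comparison of retained and lost subjects, the first set of analyses is to make no adjustment for dropout: "Only cases with complete data will be included".

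The mixed model's fixed effects, covariates, covariance structure and treatment contrast are not given. Randomization is stratified ("Participants will be stratified by site during randomization"), but site is not named as a model term. The 0.05 threshold stands in the secondary-endpoint paragraph. The statement next to it, "All tests will be two-tailed", is general, and no other level is given for the primary endpoint, so two-sided 5% is the natural reading.

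On blinding, the Endpoints section has the NPD traces read blinded to arm. The Study Drug section says: "Research pharmacists, UM biostatistician core and the assign unblinded monitor will be unblinded". Consultant Arrangements names the same core as the source of biostatistics support.

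**The concern.** A test at 0.05 has a 5% false-positive rate only if it is fixed in advance or chosen without sight of the results by arm. The third statement reopens what the second seemed to settle, and nothing limits how the choice is made. Blinded reading of traces protects the measurement but not the selection of a model. Because the core supporting the analysis is unblinded, the plan does not rule out that the method is picked by people who can see how each option turns out.

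With 36 patients, the primary result may well lie near the threshold. If two defensible analyses disagree there, a reader cannot establish whether the reported one was selected before or after that was known.

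**Working it through.** **Inputs from the documents.** 36 patients, 18 per arm, expected difference more than -4 mV (Study Design and Methods); two-sided 0.05; NPD at Visits 1, 5 and 7 (Appendix 1).

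**Inputs that are assumptions.** The supplied text has no SD, power, dropout rate or between-visit correlation, so the sample size of 36 cannot be reproduced. Solving backwards with a t-test, 18 per arm and 4 mV give 80% power if the SD of change is 4.16 mV (4 / 4.16 = 0.961 SD). Correlation is taken as equal between visits at 0.3, 0.5 or 0.7. Dropout is taken as 0, 2/18 = 11% or 4/18 = 22% missing Visit 7 per arm, completely at random, half of them also missing Visit 5.

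**Step 1: the two named analyses.**

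- t-test on the Visit 1 to Visit 7 change: t = difference in mean change / [s × √(1/18 + 1/18)], df = 36 − 2 = 34.
- Random-intercept model with arm-by-visit means, same contrast. Its residual variance is pooled over all three visits, so df = 36 × (3 − 1) − 4 = 68.

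With complete data the estimate is the same. Only the standard error and df differ, so the two p-values are close but not equal.

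**Step 2: false-positive rate under the null.** Each test used alone gave 5.0% to 5.1%.

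| Rule | Complete | 11% missing | 22% missing |
|---|---|---|---|
| Smaller p, t-test or random intercept | 5.8% | 6.2% | 6.5% |
| Smaller p, t-test or unstructured mixed model | 5.0% (identical tests) | 5.8% | 6.2% |
| Choice by completeness only, blind to arm results | – | 5.0% | 5.0% |

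The last row takes the t-test if at most 3 of 36 miss Visit 7 and the random-intercept model otherwise, at correlation 0.5 with random dropout. Runs per correlation were 1,000,000 for the first row with complete data and 100,000 with dropout. The unstructured comparison with dropout used 60,000 in all, and the completeness rule 120,000 per dropout rate.

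The result depends on the menu. The mixed model's terms are open, so a baseline-adjusted model is another candidate. The smaller p of the t-test on change and a baseline-adjusted Visit 7 model gave 7.7%, 7.1% and 6.6% at correlations 0.3, 0.5 and 0.7 with complete data (20,000 trials each).

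**Step 3: how often the choice decides significance.** At 0.961 SD (80% power for the t-test, correlation 0.5), the t-test and random-intercept model fall on opposite sides of 0.05 in 3.9% of trials with complete data, 6.8% with 11% missing and 9.9% with 22% missing.

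**Step 4: a separate point, the unnamed covariance.** This is not evidence about post hoc choice. Suppose correlation decays with time (assumption), for example 0.7 between adjacent visits and 0.49 between Visits 1 and 7.

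- The random-intercept model works with the average correlation, (0.7 + 0.7 + 0.49) / 3 = 0.63, and so takes the variance of the change as 2 × (1 − 0.63) = 0.74.
- The true value is 2 × (1 − 0.49) = 1.02.
- The standard error is too small by √(1.02 / 0.74) = 1.174. The critical value 1.995 (68 df) acts as 1.995 / 1.174 = 1.70, an error rate of about 9.4%.

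Simulation gives 9.4% for this case. Over three decay patterns, with and without missing data, the range is 8.1% to 10.0%. Naming the structure therefore matters even if the model is fixed in advance.

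**The case against.** The sentence sits between the missing-data clause and the comparison of retained with lost subjects, so it may mean only that the method will suit the amount and pattern of data available. The mixed model is already called formal and the t-test preliminary, so keeping the better of the two would contradict the plan's own labels. The inflation is small. It is nil with complete data and an unstructured model. If the mixed model uses only a pre and a post measurement, it is essentially nil with complete data (5.1%, the same as the t-test alone) and 5.6% to 6.3% with dropout. Two valid tests will always disagree sometimes, so the disagreement rates do not show bias. Nothing says that whoever selects the model will first see outcomes by arm. This is also a proof-of-concept trial.

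Much of this stands. The benign reading is plausible and, applied blind to arm results, would be harmless, as the 5.0% shows. The simulated excess is a worst case that ignores the labels. But the text does not confine itself to the benign reading, and the formal label constrains little when the model has no stated terms. The plan calls only its secondary endpoints exploratory, whereas the primary is a stated hypothesis against placebo. The objection limits the size of the problem and does not remove it.

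**Conclusion.** The concern holds: the plan permits an unrestricted, data-dependent choice of primary analysis, so the two-sided 5% level is not assured. This does not say that the level will be exceeded. If the more favourable of the two named analyses were kept, the error would be between 5.0% (complete data with an unstructured model) and about 6.5%. A wider menu with baseline adjustment would take it to about 7% to 8%. These figures rest on assumed correlations and dropout. The main harm is to the credibility of a borderline result. It should be fixed, since the effect is modest but the remedy is simple.

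Two smaller points go with it. The complete-case sentence most naturally belongs to the first set of analyses, which one clause should say. The covariance structure of the mixed model should be named.

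**What to change.** Delete the sentence that leaves the approach to the final data. Before outcomes are linked to treatment codes, fix one primary analysis and record the sign-off.

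One workable choice among several valid ones is a repeated-measures mixed model on all available post-baseline NPD responses, with:

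- treatment, visit, treatment-by-visit, baseline NPD response and site (the stratification factor);
- a covariance that does not assume equal correlation, such as unstructured with Kenward-Roger degrees of freedom and a named fallback;
- the losartan-minus-placebo contrast at Visit 7, the last NPD visit.

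In 18 scenarios of 20,000 null trials, with equal and decaying correlation and 0, 2 or 4 of 18 missing per arm, this model gave 4.8% to 5.3%.

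If adaptation to missing data is wanted, write the rule in advance and apply it without treatment codes. State that the complete-case sentence governs only the preliminary t-test, and report the t-test and complete-case results as sensitivity analyses.

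Visit 7 as week 13 is inferred, because the time labels in the Appendix 1 table are shifted in the extracted text. Supplies of 3, 3 and 8 weeks from Visits 2, 4 and 5 put Visit 4 at week 3, Visit 5 at week 3 + 3 = 6 and the end of supply at week 6 + 8 = 14. Reading the labels in visit order then gives week 13 for Visit 7, which agrees with "Means at baseline, 6 and 13/14 weeks, for each outcome". The sponsor should confirm it.

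The cost is one paragraph of wording, with no new patients or data. The sponsor gives up post hoc flexibility and, with this model, a few error degrees of freedom: a median of about 31 with complete data and 24 to 26 with 22% missing, against 34 and 28 − 2 = 26 for the t-test.
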